Results from the proposed study could increase patient recovery at little or no increased cost. Normal saline and lactated ringer's solutions (1000 ml or CC) are similar costs (1.485 and 1.304 Payment Limits, respectively)¹⁶, and both are readily available in most hospital formularies. This study proposes comparing two readily-available, low-cost IV fluids on the basis of patient-reported quality of recovery in patients discharged from the ED.

The study **hypothesis** is emergency department patients receiving lactated ringer's solution will have an improved Quality of Recovery when compared patients receiving normal saline.

C. Study Objectives

C.1. Primary Aim

The primary objective of this study is to compare the quality of recovery in ED patients receiving lactated ringer's and normal saline IV solutions at 24 hours after ED discharge.

C.2. Secondary Aim

The secondary aim of the study is to describe differences in healthcare utilization after ED discharge between subjects in the control NS and intervention LR groups.

D. Study Design

D.1. Overview & Design Summary

This is a single-blind, randomized controlled trial in a single Midwestern emergency department with 60,000 patient visits per year. Enrollment of 156 subjects is planned. Subjects will be randomized to receive a single administration of two liters of either normal saline or lactated ringer's solution. Evaluations will occur at baseline, one day following ED discharge, and seven days following ED discharge.

Potential participants will be screened upon ED registration. Subjects will participate in study for seven days (during ED visit with two remote follow-up contacts at one and seven days). Total duration of the study is expected to be 12 weeks.

D.2. Subject Selection

Subjects will be recruited in the emergency department by two trained research assistants (RAs). Subjects will be recruited beginning in May 2017.

D.2.a. Inclusion Criteria

Patients (1) with a chief complaint of: nausea, vomiting or emesis, diarrhea, abdominal pain, dizziness, weakness, heat stroke or heat exhaustion, dehydration, fatigue, or volume depletion; (2) are deemed by their ED provider to be clinically able to receive two liters of fluid; (3) are being administered fluids by their ED treatment team; and (4) are decided to be likely to be discharged from the ED are eligible for the study.

D.2.a. Exclusion Criteria

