Patients without consistent access to a phone with text-messaging capabilities for the following seven days and/or without a primary care physician will be excluded from this study. Patients from the following groups will be excluded: pregnant, prisoners, did not speak English, were undergoing current chemotherapy, signs of jaundice, already received greater than 250 mL of IV fluids, or unable to provide informed consent.

D.2.b. Subject Recruitment Plans, Screening and Consent

Screening will begin as the patient checks in to the ED with the triage nurse and enters a chief complaint. Two RAs will monitor the emergency department electronic patient list in real time to identify patients with eligible chief complaints. The RA will approach the patient's provider to determine if patient meets inclusion criteria (2-4). If the provider determines the patient meets both inclusion criteria, the RA will approach the patient in his/her ED patient room to screen the patient for eligibility based on stated inclusion and exclusion criteria.

If patient meets all inclusion criteria and does not meet any exclusion criteria, the RA will discuss the study with the patient using a standard, IRB-approved script. If the patient is agreeable to participation in the study, written consent will be obtained and proof of research participation will be documented in the patient's electronic medical record.

D.2.c. Randomization Method and Blinding

Randomization of intervention will be 1:1 in randomized, permuted blocks.

Randomization will be performed in SAS (SAS Institute), version 9.4. Blinded allocation ("Drug 1" or "Drug 2") will be placed in sealed opaque envelopes labelled by subject ID before the enrollment period begins. All research team members involved in patient enrollment and outcome assessment (survey administration) will not be involved in this randomization process.

D.3. Intervention

Following randomization, a RA will work with the nursing staff to procure the correct IV solution and administer the solution. Times of initiation and termination of fluid administration and amount of actual fluid administered will be recorded for covariate analysis.

D.3.a. Description

Both intervention and control medications will be delivered intravenously via peripheral venous access at room-temperature. Fluid administration rate will be 1,000 mL/15 minutes by pressure bag method and will be monitored by an RA.

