Intervention is 2,000 mL lactated ringer's IV solution (see description below).

"Each 100 mL of Lactated Ringer's Injection, USP contains sodium chloride 600 mg, sodium lactate, anhydrous 310 mg, potassium chloride 30 mg and calcium chloride, dihydrate 20 mg... A liter provides 9 calories (from lactate), sodium (Na⁺), 130 mEq, potassium (K⁺) 4 mEq, calcium (Ca⁺⁺) 3 mEq, chloride (Cl⁻) 109 mEq and lactate [CH₃CH(OH) COO⁻] 28 mEq. The electrolyte content is isotonic (273 mOsmol/liter, calc.) in relation to the extracellular fluid (approx. 280 mOsmol/liter). The pH of the solution is 6.6 (6.0 to 7.5)."¹⁷

Control is 2,000 mL of normal saline (0.9% sodium chloride).

D.3.b. Subject Compliance Monitoring

RAs will record time of initiation and completion of each bag of IV fluid and confirm patient is receiving correct fluid for allocation group. Any crossovers or premature stopping of fluid administration will be documented. Actual amount of fluid (mL) received will be documented.

D.3.c. Data Collection Procedures for Adverse Events

Any adverse event occurring in the ED would be recorded by the RA. Subjects will also be given contact information for a study physician, trained in emergency medicine, and will be instructed to call with concerns or to report any adverse events.

Further, an EM physician, not affiliated with the study, will be presented group data (blinded to treatment allocation) of 28-day patient medical treatment at the enrolling medical facility to assess safety for stopping. This chart review data will be collected by a research team member, blinded to subject group. Subject group ("A" or "B") will be added by study statistician (treatment ["LR" or "NS"] will not be revealed).

D.4. Study Outcome Measurements and Ascertainment

Outcomes will be recorded by trained RAs at time of ascertainment. RA obtaining outcome measurement will be blinded to subject allocation. Data will be entered and stored electronically on a secure server that can be accessed from any location at the enrolling site. Paper surveys will be saved in a locked file cabinet at the enrolling site.

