At the time of enrollment, baseline characteristics of subjects will be collected by RAs by in-person interview (pre-intervention QoR-40 score) and from electronic medical record (age, gender). Some baseline characters will be collected at the chart abstraction (ED encounter disposition [discharged from ED/admitted to hospital/admitted to ICU], ED diagnosis type [by organ system]).

D.4.a. Primary Endpoint

The primary outcome of this study will be the post-treatment survey score of the Quality of Recovery-40 (QoR-40, see Attachment H-2) validated survey tool^{18,19}. The survey has been used extensively in the surgery anesthesia literature to measure patient-

reported recovery across five independent domains: Comfort, Emotion, Physical Independence, Patient Support, and Pain. Survey scores range from 40 to 200.

RAs will administer the QoR-40 to subjects initially before any intervention is administered (“pre”). Twenty-four hours following discharge, the RAs will administer the survey again by telephone (“post”). During survey administration, RA will fill-out survey on paper, and it will later be entered into the electronic database. If patient does not answer, two additional phone calls will be made in the 24-48 hours following ED discharge. Time of “post” survey response will be recorded.

D.4.b. Secondary Endpoint

Secondary endpoints are designed to examine differences in healthcare administration between the NS control and LR intervention groups. Secondary endpoints will be assessed at two time points (1) at the 24-hour post-discharge phone call and (2) with a 7-day follow-up text message utilizing a two-way text messaging system.

The following secondary endpoints will be recorded:

- (A) Sought additional healthcare for same complaint,
- (B) Returned to an ED for same complaint,
- (C) Filled an ED prescription from visit of enrollment, and

Each endpoint will be a dichotomous (yes/no) response. No adjudication of “same complaint” will be performed by the research team, as the intention is to capture the patient’s interpretation of healthcare utilization from the illness.

D.4.c. Subgroups

No *a priori* subgroup analyses are planned. Any subgroup analyses performed will be solely for the purpose of hypothesis generation.

E. Statistical Plan

E.1. Sample Size Determination and Power

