Sample size calculation was based on the detection of a 10-point difference on the QoR-40 survey scores. A 10-pt difference was selected as the minimum detectable difference maintaining clinical relevance, as supported by previous studies¹⁸⁻²¹. Sample size calculation ($\alpha = 0.05$, $\beta = 0.90$, 20% dropout, difference of 10 points) revealed a need for 156 total subjects.

E.2. Statistical Analysis

Baseline characteristics. Baseline characteristics will be reported with summary statistics as appropriate (mean, SD, median, IQR) and differences in characteristics will be conducted using t-test for continuous variables and chi-square test for categorical variables. If any baseline characteristics have significant differences, those behaviors will be reported in the results section and an adjusted analysis will be performed on primary and secondary variables to assess the impact of the imbalances.

Primary outcome. The primary outcome, pre-post difference in Quality of Recovery-40, will be analyzed using a t-test (if parametric) or Mann Whitney U Test (non-parametric) in an intention-to-treat (ITT) analysis. Due to the nature of emergency department

research, an additional analysis will be done by treatment received and compared to the primary ITT analysis.

Secondary outcome & safety analysis. Secondary outcomes will be reported as a relative risk with 95%CI in an ITT analysis. A safety analysis of selected secondary outcomes (return to ED and seeking additional healthcare for same complaint) will be performed by treatment received.

Covariate analysis. Differences in actual fluid administered and time from intervention to primary outcome will be assessed. If significant, analysis adjusting for covariates of time from intervention to primary outcome, post-QoR-40 administration, and amount of fluid (mL) received will be performed with multivariable linear regression and multivariable logistic regression (primary and secondary outcomes, respectively).

F. Quality Control

F.1. Study Monitoring Plan

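### The conditional adjusted analyses in E.2 can adjust for variables that arise after randomisation: fluid volume received, time to outcome, and actual ED disposition, which D.4 lists as baseline

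*Combined protocol and SAP*

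**What the plan says.** Section E.2 of the combined protocol and SAP names an unadjusted ITT comparison of the pre-post QoR-40 difference as primary. Two further rules lead to adjusted models for the primary and secondary outcomes.

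- **Covariate rule (E.2, Covariate analysis).** If volume received or time to outcome differs significantly between arms, "analysis adjusting for covariates of time from intervention to primary outcome, post-QoR-40 administration, and amount of fluid (mL) received will be performed". The models are linear for the primary outcome and logistic for the secondary ones. D.3 says the "amount of actual fluid administered will be recorded for covariate analysis", and D.3.b adds: "Any crossovers or premature stopping of fluid administration will be documented". On timing, D.4.a says: "Twenty-four hours following discharge, the RAs will administer the survey again by telephone", with two more attempts allowed up to 48 hours.
- **Baseline rule (E.2, Baseline characteristics).** If any baseline characteristic differs significantly, "an adjusted analysis will be performed on primary and secondary variables to assess the impact of the imbalances". D.4 says: "Some baseline characters will be collected at the chart abstraction (ED encounter disposition [discharged from ED/admitted to hospital/admitted to ICU", with ED diagnosis type in the same list. The inclusion criteria ask only that patients "are decided to be likely to be discharged from the ED".

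Nothing restricts adjustment to variables fixed before randomisation, and nothing says which result governs if an adjusted and an ITT estimate disagree.

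**The concern.** For a true baseline variable, a significant difference between randomised arms is chance. For a variable measured after the fluid is assigned, it may be an effect of the fluid. The E.2 rules treat both cases alike, and they fire more often the more the fluid has shifted the variable.

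Disposition is the clearest case. If one fluid led to more admissions, the plan would call the difference a baseline imbalance and adjust for it, when it should be reported as a possible consequence of treatment. Adjusting for volume has a similar fault. Patients who stop early may differ in ways that also affect recovery, so comparing arms at equal volume no longer compares the groups that were randomised. Time to outcome contains the rest of the ED stay as well as the delay in reaching the patient, so it too can depend on the fluid.

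**Working it through.** **1. When each variable is fixed**

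| Variable | Source | Fixed |
|---|---|---|
| Volume received | D.3, D.3.b, H.1 | During the infusion |
| Time to outcome | D.4.a | At the follow-up call, 24–48 h after ED discharge |
| ED disposition | D.4, against the inclusion criteria | When the ED visit ends; only predicted at entry |

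All three follow randomisation.

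**2. Outcome SD**

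E.1 gives 156 subjects, 10 points, α = 0.05, 20% dropout and β = 0.90 (read as power), but no SD, so 156 cannot be reproduced from the stated inputs. Evaluable subjects are 156 × 0.8 = 124.8, about 62 per arm. With a two-sided test, SD = 10 / [(1.960 + 1.282) × √(2/62)] = 17.2. I use 17.

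**3. Volume: bias of the adjusted estimate**

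In a regression on arm and volume, the arm coefficient equals the total arm difference minus (slope on volume × arm shift in volume). With volume in SD units the slope is r × 17, so the bias is −shift × r × 17 when LR patients receive more. The within-arm correlation r is assumed.

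- r = 0.36, shifts of 0.1, 0.2, 0.3 and 0.4 SD: 0.61, 1.22, 1.84 and 2.45 points.
- Shift 0.2 SD: 0.2 × 0.2 × 17 = 0.68 points at r = 0.2, and 0.2 × 0.5 × 17 = 1.70 at r = 0.5.

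**4. Volume: effect of the trigger**

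The simulation used 200,000 trials per setting, 62 per arm, no true effect and r = 0.36. The rule fires when a t-test on volume gives p < 0.05 (E.2 states no level). Every column after the second refers to triggered trials only.

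| Shift (SD) | Rule fires | Adjusted mean | Unadjusted mean | Adjusted rejects | Unadjusted rejects |
|---|---|---|---|---|---|
| 0 | 5.0% | 0.01 | 0.00 | 5.1% | 12.0% |
| 0.1 | 8.6% | −0.62 | 1.67 | 5.3% | 9.1% |
| 0.2 | 19.7% | −1.24 | 1.50 | 7.0% | 6.9% |
| 0.3 | 38.2% | −1.83 | 1.09 | 9.4% | 5.4% |
| 0.4 | 59.8% | −2.45 | 0.70 | 13.1% | 4.9% |

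Selecting triggered trials also displaces the unadjusted estimate. Adjustment is clearly worse only from about 0.3 SD, and below 0.2 SD it does better. Over all trials the unadjusted estimate averages 0 and rejects in 5.0–5.1%.

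**5. Volume concentrated at 2,000 mL**

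Suppose early stoppers receive a uniform 500–1,900 mL, a mean shortfall of 800 mL.

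- Stopping in 10% of NS and 5% of LR: 0.05 × 800 = 40 mL, or 0.17 SD. The rule fires in 14.9% of trials, and the adjusted mean in those is −1.02.
- 15% against 5%: 0.10 × 800 = 80 mL, or 0.30 SD. It fires in 38.5%, with adjusted mean −1.83 and rejection 9.6% against 5.3% unadjusted.
- 10% in both: it fires in 4.7%, with adjusted mean 0.00.

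**6. Disposition**

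Assume two levels (admitted or not), the whole fluid effect acting through admission, and admitted patients scoring 10–20 points lower.

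- 20% NS against 10% LR admitted: the ITT difference is 0.10 × 10 = 1.0 to 0.10 × 20 = 2.0 points. The disposition-adjusted estimate is about 0.
- 10% against 5%: the ITT difference is 0.05 × 10 = 0.5 to 0.05 × 20 = 1.0 point. The adjusted estimate is again about 0.

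Probability that the chi-square rule fires (exact; without / with continuity correction):

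| Admission, NS vs LR | 62 per arm | 78 per arm (all have chart data) |
|---|---|---|
| 20% vs 10% | 33.6 / 25.9% | 42.7 / 32.8% |
| 10% vs 5% | 18.1 / 9.3% | 22.6 / 13.5% |

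**The case against.** The strongest reply is that no confirmatory result changes. The ITT comparison is named as primary, the secondary relative risks are also ITT, and the criticised models are additional and run only if triggered. That stands, and it is why the point is minor. It does not make a post-randomisation variable a baseline one.

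Next, nothing in the documents suggests that fluid type alters the volume received. Both arms are assigned the same volume at the same monitored rate, and recording early stopping does not imply that it differs by arm. That also stands. Every shift above is an assumption, and at small shifts adjustment does no harm.

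The calculations are also simpler than the plan. They trigger on and adjust for volume alone, whereas E.2 uses volume and time together. The near-zero adjusted estimate for disposition follows from sending the whole effect through admission. The plan does not say how admitted patients are surveyed. If they give no post score, adjusting QoR-40 for disposition among responders hardly matters, and the problem becomes one of missing outcomes. These points limit the figures to illustrations but leave the rule as written.

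Finally, calls may fall anywhere between 24 and 48 hours, so looking at measurement time is reasonable. It can be reported by arm, or modelled if labelled exploratory. E.2's statement that "an additional analysis will be done by treatment received and compared to the primary ITT analysis" concerns the treatment-received analysis, so it does not settle how these adjusted models should be read.

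**Conclusion.** The concern holds. E.2 can adjust for volume received and time to outcome, and, through the D.4 list, for actual ED disposition. If the assigned fluid shifts one of these, and the variable affects or shares causes with the outcome, the adjusted estimate no longer estimates the randomised LR–NS effect. If the fluid does not shift the variable, the adjusted estimate is unbiased.

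The true size cannot be known from the documents. The illustrations give 0.6–2.4 points for volume shifts of 0.1–0.4 SD (r = 0.36, SD 17) and 0.5–2.0 points for disposition, against a 10-point target. No size is estimated for time to outcome or for the secondary outcomes. The severity is minor because the unadjusted ITT analyses are untouched.

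**What to change.** 1. Take ED disposition out of the baseline list in D.4 and out of the E.2 adjustment trigger, and report it by arm as a post-randomisation outcome. Report ED diagnosis type descriptively, since it comes from the same chart abstraction, and adjust for it only if it was fixed before randomisation.
2. Report volume received and time to outcome by arm. If the model adjusting for them is kept, state that it is exploratory, that it conditions on post-randomisation variables, and that the ITT result governs. Make clear that the mention of post-QoR-40 administration only marks the end of the time interval; read as the post score, it would put the outcome among the covariates.
3. Limit any supportive adjusted analysis to pre-intervention QoR-40, age and gender, specified in advance and not triggered by a significance test.

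The cost is wording only: every variable is already collected and the sample size does not change. The disposition-adjusted estimate is lost, and the volume- and time-adjusted estimates are dropped or become exploratory.
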